APPENDIX E – Expected Adverse Events for Cytarabine and/or Idarubicin

For this protocol only, certain AEs/Toxicity Grades are exceptions to the Expedited Reporting Guidelines because the AEs are considered as “Expected” with the administration of cytarabine and idarubicin. The following AEs must be reported through the routine AE or SAE reporting mechanism, as appropriate:

CTCAE Category	Adverse Event	Grade	Chemotherapy Attribution
Blood & Lymphatic	Bone marrow suppression/failure	1-4	 cytarabine  idarubicin
	Neutropenia	1-4	 cytarabine
	Febrile neutropenia	3-4	 idarubicin
	Thrombocytopenia	1-4	 cytarabine  idarubicin
	Pancytopenia	1-4	 cytarabine  idarubicin
	Reticulocyte count, decreased	1-4	 cytarabine  idarubicin
	Hemorrhage/bleeding (secondary to thrombocytopenia)	1-4	 cytarabine  idarubicin
General Disorders	Anemia	1-4	 cytarabine
	Anemia (megaloblastic)	1-2	 idarubicin
	Fatigue	1-3	 cytarabine  idarubicin
	Fever	1-4	 cytarabine  idarubicin
General Disorders	Chills	1-3	 cytarabine  idarubicin
	Injection site reaction/cellulitis, pain, stinging or burning sensation, inflammation	1-4	 cytarabine  idarubicin

CTCAE Category	Adverse Event	Grade	Chemotherapy Attribution
	Tissue necrosis (if extravasation)	3-4	 cytarabine  idarubicin
	Infections	1-4	 cytarabine  idarubicin
	Edema/swelling	1-3	 cytarabine  idarubicin
Respiratory, Thoracic and Mediastinal Disorders	Pulmonary toxicity	1-4	 cytarabine  idarubicin
	Dyspnea	1-4	 cytarabine  idarubicin
	Adult respiratory distress syndrome (ARDS)	3-4	 cytarabine  idarubicin
	Pulmonary edema	1-4	 cytarabine  idarubicin
	Oropharyngeal pain	1-4	 cytarabine  idarubicin
	Pulmonary allergy	1-4	 idarubicin
	Interstitial pneumonitis	2-4	 cytarabine  idarubicin
Gastrointestinal Disorders	Diarrhea	1-4	 cytarabine  idarubicin
	Bowel necrosis	3-4	 cytarabine
	Necrotizing colitis	3-4	 cytarabine
	Abdominal or stomach pain/tenderness/cramping	1-3	 cytarabine  idarubicin

CTCAE Category	Adverse Event	Grade	Chemotherapy Attribution
	(peritonitis)		
	Typhlitis (neutropenic enterocolitis)	3-4	 cytarabine  idarubicin
	Pneumatosis intestinalis	1-4	 cytarabine
	Nausea	1-3	 cytarabine  idarubicin
	Vomiting	1-4	 cytarabine  idarubicin
	Ulceration/Inflammation: Oral ulcer/stomatitis/mouth, throat Esophageal ulcer/esophagitis Anal ulcer/inflammation Other GI ulceration	1-4	 cytarabine  idarubicin
	Pancreatitis	1-4	 cytarabine  idarubicin
	Hyperuricemia	1-4	 cytarabine  idarubicin
	Mucositis	1-4	 cytarabine  idarubicin
Vascular	Hypotension	1-2	 cytarabine  idarubicin
Eye Disorders	Corneal toxicity (ocular pain, tearing, foreign-body sensation, photophobia, blurred vision)	2-4	 cytarabine  idarubicin
	Hemorrhagic conjunctivitis	1-4	 cytarabine  idarubicin

CTCAE Category	Adverse Event	Grade	Chemotherapy Attribution
Hepatobiliary	Hepatic failure	3-4	 cytarabine
	Hepatic function, abnormal	3-4	 cytarabine  idarubicin
	Liver abscess/ injury	3-4	 cytarabine
	Jaundice (hyperbilirubinemia)	3-4	 cytarabine  idarubicin
	Aplasia	1-4	 idarubicin
Cardiovascular	Cardiomyopathy	1-4	 cytarabine  idarubicin
	Cardiomegaly	1-4	 cytarabine  idarubicin
	Congestive heart failure (CHF)		 idarubicin
	Left ventricular ejection fraction (LVEF), decreased	2-4 Use %drop from baseline	 idarubicin
	Arrhythmias (atrial fibrillation/others)	1-4	 idarubicin
	Abnormal ECG	1-4	 cytarabine  idarubicin
	Cardiac arrest	4	 cytarabine  idarubicin
	Chest pain	1-3	 cytarabine  idarubicin
	Myocardial infarction	2-4	 cytarabine

CTCAE Category	Adverse Event	Grade	Chemotherapy Attribution
			 idarubicin
Infections and Infestations	Infection (secondary to neutropenia/granulocytopenia)	2-4	 cytarabine  idarubicin
	Sepsis	4	 cytarabine  idarubicin
	Pneumonia	2-4	 cytarabine  idarubicin
Immune System Disorders	Anaphylaxis/Allergic edema	1-4	 cytarabine  idarubicin
Metabolism	Anorexia (decreased appetite)	2-4	 cytarabine  idarubicin
Investigations/ Laboratory Abnormalities	ALT	1-4	 cytarabine  idarubicin
	AST	1-4	 cytarabine  idarubicin
	Alkaline Phosphatase	1-4	 cytarabine  idarubicin
	GGT	1-4	 cytarabine  idarubicin
	Bilirubin, increased	1-4	 cytarabine  idarubicin
	Creatinine, increased	2-4	 idarubicin
	Uric acid, increased	1-4	 cytarabine  idarubicin
	Proteinuria	1-3	 cytarabine  idarubicin
	Electrolyte abnormalities	1-4	 cytarabine  idarubicin

CTCAE Category	Adverse Event	Grade	Chemotherapy Attribution
	Platelet count, decreased	1-4	 cytarabine  idarubicin
	WBC, decreased	1-4	 cytarabine  idarubicin
Musculoskeletal, Connective Tissue and Bone Disorders	Myalgias & Arthralgias (muscle pain/joint pain)	1-3	 cytarabine  idarubicin
	Cytarabine Syndrome: Fever, myalgia, bone pain, chest pain, rash, conjunctivities and malaise 6-12 hours following drug administration.	1-3	 cytarabine
Nervous System Disorders ^a	Paresthesia	1-3	 cytarabine  idarubicin
	Sensory peripheral neuropathy and/or motor peripheral neuropathy	1-4	 cytarabine  idarubicin
	Neuralgia/neuritis	1-3	 cytarabine  idarubicin
	Dizziness	1-3	 cytarabine  idarubicin
	Depressed Level of Consciousness (Mental Status Changes)		 idarubicin
	Seizures	1-4	 cytarabine  idarubicin
	Headache	1-3	 cytarabine  idarubicin
	Syncope/fainting	3	 cytarabine

CTCAE Category	Adverse Event	Grade	Chemotherapy Attribution
			 idarubicin
	Cerebellar and cerebral dysfunction, including the following AE/SAEs: 
 • Personality changes • Somnolence • Convulsion • Coma • Stroke-like episodes 	1-4	 cytarabine  idarubicin
Renal & Urinary	Acute kidney injury	1-4	 cytarabine
	Renal impairment, disorder	1-4	 cytarabine  idarubicin
	Urinary retention	1-4	 cytarabine  idarubicin
	Hemolytic uremic syndrome	1 or 3	 cytarabine  idarubicin
	Hyperuricemia	1,3-4	 cytarabine  idarubicin
Skin	Alopecia	1-2	 cytarabine  idarubicin
	Rash	1-3	 cytarabine  idarubicin
	Hand-foot syndrome/Palmar plantar erythrodysesthesia (PPE) (redness, swelling, pain on palms of hands/soles of feet)	1-3	 cytarabine  idarubicin
	Ulceration, skin	1-4	 cytarabine

CTCAE Category	Adverse Event	Grade	Chemotherapy Attribution
	Desquamation, peeling, scaly, exfoliation of skin	1-4	 cytarabine
	Urticaria/Hives, skin	1-3	 cytarabine  idarubicin
	Pruritis, skin	1-3	 cytarabine
	Freckling, skin	1-3	 cytarabine
Reproductive and Fertility	Teratogenicity, Embryotoxicity	4	 cytarabine  idarubicin
	Sperm abnormalities	4	 cytarabine
Congenital	Distal limb defects (upper and lower extremities) Ear deformities	4	 cytarabine  idarubicin

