PGX-ODSH-2006	II	Exacerbation of COPD	N=156, equally randomized to receive standard treatment of COPD with or without CX-01	CX-01 given as a 8 mg/kg bolus followed by CX-01, 0.375 mg/kg/h for 96 hours	
Primary Composite of failure to discharge from hospital in a timely manner + relapse within 21 days of hospital discharge
 
Secondary FEV₁, FEV₁/FVC, Borg CR10Scale, 6-minute Walk Test, BODE index and hs-CRP
	
There was no evidence of effect or efficacy of CX-01 compared to placebo for the primary endpoint for Intent-to-Treat (ITT) or Per Protocol (PP) Populations. No statistical significant effects were shown for the secondary endpoints.
 
CX-01 was well tolerated. A few instances of minor/moderate bleeding and only one case of major bleeding. Some predictable changes were noted for AST and ALT with CX-01 treatment. No other clinical and laboratory parameters showed

Study Number	Phase	Indication	Number of Patients	Study Drug and Dose	Study Endpoints	Study Results
						significant changes from baseline. Eight deaths were reported (placebo=5 and CX-01=3). Those three were not related to CX-01 occurred post treatment.
PGX-ODSH-2009-PLE	II	Protein losing enteropathy (PLE) secondary to Fontan procedure	N=5, Pediatric and young adult population	CX-01, 96 hour IV infusion at 0.125 mg/kg/h or CX-01, 96 hour IV infusion at 0.250 mg/kg/h	Safety, reduction of symptoms of PLE, reduction of alpha-1 antitrypsin levels	Though all patients had some subjective clinical improvement, CX-01 did not show clear effects on efficacy biomarkers. Due to extremely low patient enrollment and a lack of efficacy, the study was terminated early. 22 AEs and two unrelated SAEs were reported. All AEs were considered mild or moderate in intensity.

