6.6.3.2.3 Suspected Unexpected Serious Adverse Reactions

Suspected unexpected serious adverse reactions (SUSARs) are serious events that are not listed in the IB. Suspected adverse reactions means any AE for which there is a reasonable possibility that the drug caused the AE. For the purposes of Investigational New Drug (IND) safety reporting, 'reasonable possibility' means there is evidence to suggest a causal relationship between the drug and the AE.

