6.8.10 Safety Analysis

Safety analysis will be descriptive based on the Safety Population and will involve examination of descriptive statistics and individual patient listings for effects of study treatment on clinical safety and tolerability. The safety assessment period is from the first dose of study treatment until 30 days following the last dose of study treatment.

6.8.10.1 *Adverse Events*

All AEs will be categorized by SOC and Preferred Term using the MedDRA dictionary

and graded according to NCI-CTCAE v4.03. Treatment-emergent AE summaries will include NCI-CTCAE Grade 3 or higher AEs, and AEs resulting in discontinuation of study treatment, AEs resulting in death, deaths during the treatment period within 30 days of the last study treatment, deaths reported beyond 30 days that are considered study drug-related, and the incidence of laboratory values with NCI-CTCAE Grades 3 or 4. Particular attention will be upon coagulation parameters and bleeding-related events.

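### The SAP has no grouped bleeding summary although the protocol promises particular attention to bleeding, and Appendix E does not say how its expedited-reporting exception applies to events suspected to be due to CX-01

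*Protocol*

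**What the plan says.** **Bleeding in the safety analysis.** The synopsis and protocol Section 6.8.10.1 commit the analysis: "Particular attention will be upon coagulation parameters and bleeding-related events". SAP Section 7.7.1 summarises treatment-emergent events by organ class and preferred term, by grade, relatedness and seriousness, and for discontinuation and death. SAP Section 7.7.2 adds laboratory tables and graphs, including PT/INR, aPTT, anti-factor Xa and platelets. The SAP mentions bleeding only in the exclusion criteria it repeats from the protocol.

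**Expedited reporting.** Appendix E, headed as the expected events for cytarabine and/or idarubicin, says "certain AEs/Toxicity Grades are exceptions to the Expedited Reporting Guidelines because the AEs are considered as" expected with those two drugs. It then directs: "The following AEs must be reported through the routine AE or SAE reporting mechanism, as appropriate". Its attribution column offers only the two chemotherapy drugs. The rows include:

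- "Hemorrhage/bleeding (secondary to thrombocytopenia"), Grade 1-4;
- "Hepatic function, abnormal", along with hepatic failure, liver injury and jaundice, all Grade 3-4;
- "Bilirubin, increased", along with ALT, AST, GGT and alkaline phosphatase, all Grade 1-4.

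Section 6.6.3.2.3 uses a different reference: "Suspected unexpected serious adverse reactions (SUSARs) are serious events that are not listed in the IB". Section 6.6.4.1 also places expectedness for CX-01 in the IB. Section 6.6.4 sends every serious event to the CRO within 24 hours, whatever its relationship to study drug.

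**The concern.** CX-01 is a heparin derivative, and safety is one of the two primary objectives. The protocol links the drug to bleeding: hemorrhage was the only adverse effect in the animal studies (Section 4.3.1), and Table 4-1 reports for the COPD study "A few instances of minor/moderate bleeding and only one case of major bleeding". It also links CX-01 to liver-test changes, in the COPD row of Table 4-1 and as a heparin class effect in Section 7.

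Two things follow. First, if bleeds are split over many preferred terms and several organ classes, a real excess in an arm of 25 may not stand out in any row, and no planned table would put it back together. Second, a serious liver event suspected to be due to CX-01 can meet two rules. Appendix E excepts it because chemotherapy can cause it, while Section 6.6.3.2.3 asks only whether the IB lists it. The documents do not say which rule governs.

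**Working it through.** The plan gives no figure on this point to reproduce. The check is a comparison of texts, plus one illustration.

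**1. Promise against delivery**

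| Item | Protocol 6.8.10.1 | SAP |
|---|---|---|
| Coagulation parameters | particular attention | tables and graphs (7.7.2) |
| Bleeding-related events | particular attention | no grouping in 7.7.1 or the Appendix II table list |
| Declared as a change | not applicable | not in Section 8 |

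Table 14.3.1.4 counts CX-01-related events by grade, not by type, so it does not fill the gap.

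**2. What grouping could be worth**

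The only input from the documents is 25 patients per arm (protocol 6.8.1). Everything else is assumed: bleeding risk 20% in control and 50% (or 45%) in the higher-dose arm, one bleed per affected patient, and each bleed falling into one of eight equally likely terms.

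Expected patients with a bleed: 25 × 0.50 = 12.5 against 25 × 0.20 = 5, a difference of 7.5. Per term, the difference is 7.5 / 8 = 0.94 patients.

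- Grouped row, exact: P(Y − X ≥ d) = Σₓ Bin(x; 25, p₀) × P(Y ≥ x + d), with Y ~ Bin(25, p₁).
- Term rows, simulated (400,000 trials): the chance that at least one term row shows a difference of 4 or more.
- False alarm: the same quantities with p₁ = p₀ = 20%.

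With a threshold of 4 for both, the grouped row shows the excess in 89% of trials and some term row does in 31% (81% and 23% at 45%). That comparison is unfair, because the false-alarm rates are 11% and 1.5%. The table raises the grouped threshold to bring the rates close.

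| Assumed terms and risks | Any term row, ≥4: false alarm / shows excess | Grouped row: threshold, false alarm / shows excess |
|---|---|---|
| 8 equal, 20% v 50% | 1.5% / 31% | ≥7, 1.0% / 63% |
| 8 equal, 20% v 45% | 1.5% / 23% | ≥7, 1.0% / 47% |
| 4 equal, 20% v 50% | 4.9% / 63% | ≥5, 5.5% / 83% |
| 8 unequal (40/20/10/10/5/5/5/5%), 20% v 50% | 4.1% / 54% | ≥6, 2.5% / 74% |

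Grouping does better in each setting, but the ratio falls from about two (63/31) to about 1.3 (83/63) with four terms.

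**3. The two expectedness rules**

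Take a serious event that is listed in Appendix E, suspected to be related to CX-01, and absent from the IB. Under 6.6.3.2.3 it is a SUSAR. Under Appendix E it is excepted from expedited reporting. Section 6.6.4.4 refers to applicable rules and does not rank the two. If the IB does list the event, it is expected under both rules and there is no conflict.

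The liver rows carry no limit on cause, so the overlap is plain there. The bleeding row is limited to bleeding secondary to thrombocytopenia, so bleeding from an anticoagulant effect falls outside its wording, although the two may be hard to separate during induction.

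**The case against.** The strongest reply on reporting is that expectedness is already divided by drug. Appendix E is titled and columned for chemotherapy, Section 6.6.4.1 gives CX-01 to the IB, and Section 6.6.3.2.1 requires the relationship to AML, chemotherapy and CX-01 to be assessed for each event. This stands in part. A reader might infer that Appendix E exempts events even when they are attributed to CX-01. It does not say so; that reading rests on silence. What remains is a missing cross-reference.

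A reader might also infer that serious CX-01 reactions would be withheld from regulators and sites. The documents do not support that. Serious events reach the CRO within 24 hours, the numeric grade ranges in Appendix E stop at Grade 4, and the outcome depends on the IB and the reporting guidelines, neither of which is supplied. Section 4.3.1 calls hemorrhage expected and Table 4-1 calls the AST/ALT changes predictable, so the IB may well list both. Nor does the appearance of anaphylaxis and stroke-like episodes in Appendix E make them CX-01 risks; the protocol does not link either to the drug.

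On the SAP, it can be said that particular attention is not a promise of a grouped table, that listings and organ-class tables will exist, that the shells allow added tables, and that the DSMC's tables are set in a separate charter. All true. But a grouping chosen after the data are seen is weaker than a pre-specified one, and nothing in the SAP acts on the bleeding half of the commitment.

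**Conclusion.** Both parts hold in a limited form. The SAP part needs no inference: the protocol singles out bleeding-related events, the SAP provides no summary of them as a group, and it does not record the difference. The size of the benefit is illustrative only. About 63% against 31% at similar false-alarm rates rests on assumed risks, one bleed per patient and eight equal terms; it ignores organ-class rows and shrinks with fewer or unequal terms. The figures 89% and 31% should not be used as the contrast, because the common threshold favours grouping.

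The Appendix E part is an unreconciled pair of rules, clearest for liver events and narrower for bleeding. Its consequence is limited to onward expedited reporting of non-fatal serious events suspected to be due to CX-01, and whether any such report would change cannot be settled from these documents.

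**What to change.** 1. **SAP 7.7.1:** add one pre-specified grouped bleeding row, defined by the standard MedDRA haemorrhage query in the version already used (14.1) or by a fixed term list. Show any-grade, Grade 3 or higher, and serious treatment-emergent events by arm, and supply the same row to the DSMC. Cost: one extra table from data already collected.

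2. **Appendix E:** add a sentence saying that the exception does not apply to serious events suspected to be related to CX-01, for which Section 6.6.3.2.3 and the IB govern, and cross-refer to Section 6.6.4.1. Cost: one sentence, and possibly a few more expedited reports for the sponsor to process.

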APPENDIX F – Blood Sample Handling

Blood sample collection procedure, and sample process, storage and shipment

- The study site will be provided with 4.5 mL tubes with 3.2% trisodium citrate
- Draw and fill the 4.5 mL tube containing 3.2% trisodium citrate (completely fill with blood to minimize citrate dilution)
- Within 30 minutes of collection, centrifuge tube for 15 minutes at 3000 g at 16°C/ 60.8°F. **Blood samples must be kept on ice until they are centrifuged (a delay in centrifuging and separating plasma should not exceed one hour because the platelet factor leaches out of platelets and binds CX-01 resulting in erroneous CX-01 values)**
- Using a plastic pipette, transfer 2 mL of plasma from the tube into two provided cryogenic vials; 1 mL in each tube. Each of the two 1 mL-cryogenic vials must be labeled:

"CX-01 concentration" and will also include: The sample #, patient's randomization/Study ID #, Initials, Study site #, Protocol # (CNTX-CX-01-2015-AML-2) and collection date/time.

- Labeled 1 mL/cryogenic tubes must be stored immediately in a -60°C to 80°C freezer

Once the full set of blood samples from a patient is complete, all the resulting vials must be shipped under cryogenic conditions (dry ice) to the bioanalytical laboratory (see Study Operations Manual for name of lab and notification number).

Please call the bioanalytical laboratory to notify them prior to shipments. Please ship specimens via FedEx only on Monday, Tuesday or Wednesday to prevent thawing and sample loss.

1 SOURCE DOCUMENTS

The Statistical Analysis Plan (SAP) was written based on the following documentation:

Document	Date	Version
Protocol	04 February 2016	1.0
Protocol Amendment 1	16 September 2016	2.0
Protocol Amendment 2	13 January 2017	3.0
eCRF	25 July 2016	1.0
eCRF Amendment	16 August 2017	1.0.4

2 PROTOCOL DETAILS

2.1 Study Objectives

This randomized, phase II study of CX-01 is designed to assess the effect of adding CX-01 at one of the two different dose levels to standard induction and consolidation therapy for newly diagnosed patients with AML.

2.2 Primary Objectives

The primary objectives are:

- To assess whether 2-0, 3-0 desulfated heparin (CX-01), administered at any or all studied dose levels in conjunction with standard induction therapy for AML increases the morphologic complete remission (CR) rate based on International Working Group (IWG) criteria.
- To assess the safety and tolerability of CX-01, administered at two studied dose levels in conjunction with standard induction therapy for AML.

2.3 Secondary Objectives

The secondary efficacy objectives are:

To assess whether CX-01, administered at any or all studied dose levels in conjunction with standard induction and consolidation therapy for AML improves:

- Event-free survival (EFS)
- Leukemia-free survival (LFS)
- Overall survival (OS)

Statistical Analysis Plan

Version: Final

Date of Issue: 20 March 2018

Cantex Pharmaceuticals, Inc. Protocol No. CNTX-CX-01 2015 AML I Covance Study ID: 00000014620 I

- Composite CR rate: incidence of CR+ CRi+CRp
- Duration of morphologic CR
- 30-day mortality (in the induction cycle)
- 60-day mortality (in the induction cycle)
- 90-day mortality (in the induction cycle)
- Days until neutrophil recovery to $> 1,000/\mu\text{L}$
- Days until platelet recovery to $> 100,000/\mu\text{L}$

2.4 Exploratory Objectives

The following items are not specified in the protocol but are still of clinical importance and will be analyzed:

- Duration of composite CR (if present)
- Days until neutrophil recovery to $> 500/\mu\text{L}$
- Days until platelet recovery to $> 20,000/\mu\text{L}$

2.5 Overall Study Design

This is an exploratory phase II, open-label, randomized, multicenter, parallel group trial to determine whether there is evidence that the addition of either or both different dose levels of CX-01 to standard induction therapy (idarubicin + cytarabine) and consolidation therapy has an additive therapeutic effect in newly diagnosed AML patients when compared to patients receiving standard induction chemotherapy alone.

To be eligible to participate in the study, patients must meet the following criteria:

1. Newly diagnosed, de novo or secondary, previously untreated AML
2. Age 60 or above
3. Eastern Cooperative Oncology Group (ECOG) performance status of 0 or 1
4. Cardiac ejection fraction $\geq 45\%$ (as determined by echocardiography or multi-gated acquisition scan)
5. Adequate hepatic and renal function determined by the following laboratory values:
 - Aspartate aminotransferase (AST) or alanine aminotransferase (ALT) $< 2.5 \times$ upper limit of normal (ULN)

Statistical Analysis Plan

Version: Final

Date of Issue: 20 March 2018

Cantex Pharmaceuticals, Inc. Protocol No. CNTX-CX-01 2015 AML I Covance Study ID: 000000146201

- Bilirubin <2.5 x ULN
- Calculated creatinine clearance by Cockcroft Gault formula >30 mL/min.
- 6. Able to provide informed consent and have signed an approved consent form that conforms to federal and institutional guidelines.

Patients who meet any of the following criteria will not be eligible to participate in the study:

1. Patients with acute promyelocytic leukemia based on the presence of t(15; 17)(q22;q 12) as determined by karyotyping, fluorescence in situ hybridization or polymerase chain reaction
2. Prior chemotherapy for AML (including investigational therapy); prior hydroxyurea to control white blood cell count and a single intrathecal administration of cytarabine for CNS prophylaxis is allowed
3. Prior intensive chemotherapy or stem cell transplantation for treatment of myelodysplastic syndrome (prior treatment with hypomethylating agents and lenalidomide are allowed)
4. Presence of central nervous system leukemia
5. Presence of significant active infection that is not controlled in the opinion of the Investigator
6. Presence of significant active bleeding
7. History of severe congestive heart failure or other cardiac disease that contraindicates the use of anthracyclines, including idarubicin
8. Pre-existing liver disease (such as CHILD-Pugh Class B or C liver disease)
9. Renal insufficiency which might adversely affect schedule and dose of therapy with cytarabine as well as management of tumor lysis syndrome
10. History of drug addiction within the last 6 months
11. Known history of positive Hepatitis B surface antigens
12. Known history of positive test for Human Immunodeficiency Virus antibodies
13. Psychiatric or neurologic conditions that could compromise patient safety or compliance, or interfere with the ability to give proper informed consent
14. History of other active malignant disease within the past 3 years, other than cured basal cell carcinoma of the skin, cured in situ carcinoma of the cervix, or localized prostate cancer that has received definitive therapy. Such prostate cancer patients who are receiving hormonal therapy are eligible
15. Patients receiving any form of anticoagulant therapy (heparin flushes for IV catheter permitted)
16. Presence of a known bleeding disorder or coagulation abnormality (including but not limited to a PTT >40 seconds) or any condition that requires maintenance of platelet counts at 50,000/ μ L or higher
17. Pregnant or breast feeding patients
18. Patients of childbearing potential not using adequate contraception.

Approximately 75 patients will be randomized in a 1:1:1 ratio to one of the following study treatment groups:

Statistical Analysis Plan

Version: Final

Date of Issue: 20 March 2018

Cantex Pharmaceuticals, Inc. Protocol No. CNTX-CX-0 I 2015 AML I Covance Study ID: 00000014620 I

- **Group 1:** Idarubicin + Cytarabine, OR
- **Group 2:** Idarubicin + Cytarabine plus lower dose CX-01 (0.125 mg/kg/hour), OR
- **Group 3:** Idarubicin + Cytarabine plus higher dose CX-0 I (0.25 mg/kg/hour)

Eligible patients who meet the inclusion criteria and do not meet any of the exclusion criteria and have provided informed consent will be enrolled in the study. Each patient will participate in the study for approximately 18 months from the time of informed consent through final study contact, or until they withdraw from the study or the study is terminated by the Sponsor.

Overall survival data will be collected every 3 months until death or until the end of study by the investigational sites. The end of study will occur approximately 18 months after the last patient is randomized. Overall survival data will be collected every 3 months until death or until the end of study by the investigational sites. The end of study will occur approximately 18 months after the last patient is randomized.

A Data and Safety Monitoring Committee (DSMC) will meet periodically to review the safety of the study (see Section 6.6.5 of protocol). Details describing the DSMC process and procedures will be outlined in a separate DSMC Charter.

Adverse events (AEs) will be collected from time of informed consent and continue until 30 days after the last study treatment is administered. Longer follow-up and collection of AEs may be required for patients that do not have an absolute neutrophil count (ANC) recovery within 42 days (i.e., until the recovery or the reason for no recovery is diagnosed) after the last induction or consolidation cycle.

A flow diagram of the study design is shown in Figure 2---1.

[figure not shown]
Statistical Analysis Plan

Version: Final

Date of Issue: 20 March 2018

Cantex Pharmaceuticals, Inc. Protocol No. CNTX-CX-0 I 2015 AML I Covance Study ID: 00000014620 I

Figure 2---1 Study Design

Abbreviations: AML=acute myeloid leukemia

Note: It is expected that approximately 90 patients will be screened to identify 75 patients for randomization.

